The objective of this randomized controlled trial is to investigate if motivational interviewing provided as an add-on intervention to a physical activity intervention will increase the average daily step count in community-dwelling participants above the age of 70.

1. It is hypothesized that motivational interviewing, will enhance the average daily step count among participants.
2. It is hypothesized that motivational interviewing, will affect self-reported physical activity and quality of life.
3. It is hypothesized that self-efficacy and outcome expectancy for exercise, will mediate the effect and explain heterogeneity in the results.

8. Trial design

Study Type: Interventional

Estimated Enrollment: 154 participants

Allocation: Randomized

Intervention Model: Parallel Assignment

12-week intervention with two groups in a parallel design

Masking: Double (Investigator, Outcomes Assessor)

Primary investigator will be blinded for allocation before making the final analyses. No outcome assessments will be made by an assessor. Only objectively measured steps per day and participant reported outcome measures will be used for this study.

Primary Purpose: Prevention

The primary hypothesis will be investigated with a superiority analysis.

Methods: Participants, interventions, and outcomes

9. Study setting

Description of study settings (e.g., community clinic, academic hospital) and list of countries where data will be collected. Reference to where list of study sites can be obtained'.

This RCT will be conducted in Denmark. Participants eligible for inclusion will receive the content necessary for participation by mail. The participants will only have contact with the research team via phone or e-mail correspondence.

10. Eligibility criteria

Participants will be considered eligible for inclusion if they; 1) are retired and community-dwelling, 2) at least 70 years of age by the day of enrolling the trial, 3) own a smartphone or tablet able to install the *Garmin Connect application*, 4) have an email address and are able to correspond and complete the study survey on a computer and 5) have hearing abilities sufficient to receive a telephone interview.

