The 42-items questionnaire was developed originally in Danish in 1999 [51] and measures the structural aspect of social relations, with focus on contact frequency and diversity, and functional aspects with focus on perceived social support. CSRQ has been used in several Danish population-based surveys including in the Copenhagen Aging and Midlife Biobank (CAMB) [52]. In a sample of 38-69 old adults the CSRQ showed acceptable face and content validity and good test-retest reliability by 41% of the items had substantial to almost perfect agreement (kappa: 0.65-0.97) and the rest showed moderate agreement (kappa: 0.41-0.60) [53].

The secondary outcomes will also serve as follow up measurements six and 12 months after ending the intervention. They will also be conducted with online surveys.

13. Participant timeline

Time schedule of enrolment, interventions (including any run-ins and washouts), assessments, and visits for participants. A schematic diagram is highly recommended (see Figure).

[figure not shown]

Figure 1. SPIRIT participant timeline.

14. Sample size

Estimated number of participants needed to achieve study objectives is 128 participants. The number will be enough to show a 0.5 standard deviation difference between groups, equal to a moderate effect size. The number of participants will yield a power on 80% with a significance level on 0.05. To account for attrition this study will include 20% more participants than the above mentioned, and hence terminate the inclusion of participants when 154 participants in total and 77 in each group have been enrolled.

15. Recruitment

We will recruit participants through online advertisements on social media and in non-profit organizations working with older adults. We will also try to recruit participants at activity centers and other communities of older adults.

Methods: Assignment of interventions

16. Allocation

16.a. Sequence generation

Participants will be randomly assigned to either the intervention or the control group, with a 1:1 allocation. Eligible participants who have completed the baseline step count, will be randomized in blocks of four participants or more, stratified on sex (M/F) and average baseline step count for the extracted days prior to the allocation. Randomization of participants will happen every week, except weeks with less than four new participants.

16.b Allocation concealment mechanism

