Participants will be randomized using STATA, which is a statistical software package. Allocation concealment will be ensured, as the allocation will not be available until the patient has been recruited into the trial, which takes place after the baseline step count measurements have been completed.

16.c Implementation

One investigator will be in charge of the randomization. That investigator will receive a list of participant IDs every week and randomize the participants according to the above. That one investigator will not have anything do to with recruitment nor statistical analyses.

17. Blinding (masking)

17. a

Outcome assessors and data-analysts will be blinded for participant allocation.

17b.

Due to the nature of the intervention neither participants nor staff conducting the motivational interview in the intervention group can be blinded to allocation but are strongly inculcated not to disclose the allocation status of the participants with the principal investigator who will conduct the analyses. The group names of the intervention and the control group will be anonymized before the data will be analyzed to ensure blinding of the principal investigator.

Methods: Data collection, management, and analysis

18. Data collection methods

18a. Plans for assessment and collection of outcomes

Primary outcome

The primary outcome (average steps per day in the 12-week intervention period) will be extracted from the data management software Fitrockr. Participants will be asked to synchronize their PAMs and their Garmin Connect application daily, ensuring daily storage of the step counts. The PAMs have a 30-day storage for daily totals so data will not be lost, even if the participants forget to synchronize their PAMs for longer periods of time. Fitrockr will extract the data from Garmin Connect and make daily step counts available for export through their service. When the participant has completed the 12-week intervention, the daily totals will be extracted as 84 variables (12*7). After the data extraction, the average daily step count will be calculated.

Secondary outcomes

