The secondary outcomes are all participant reported and administered through SurveyXact. All participants will receive an email with an electronic SurveyXact invitation on the day of randomization. On the last day of intervention (day 84), the participants will receive a similar SurveyXact invitation with the end-point questionnaire. The six and 12-month follow up assessments will be administered in similar ways to the end-point assessment.

Demographic and other baseline items

Non-outcome variables will be included in the baseline questionnaire.

18b. Plans to promote participant retention and complete follow-up.

If possible, reasons for drop out will be collected from each discontinued participant. The available data on the primary outcome will be used to calculate the intervention period average steps per day. If the participant fails to synchronize the PAM and a possible drop out is suspected, a person from the research team will call the participant to either remind them to synchronize the PAM or try to motivate the participant to continue the intervention.

Lost to follow up with the end-point or follow up questionnaires will be reminded via email 7, 14 and 21 days after the deadline.

19. Data management

All outcomes will be handled and stored electronically.

Steps per day will be stored every time the participant synchronizes the PAM. The data handling responsible Fitrockr will extract data from the Garmin applications and store it according to the agreements. Every time a participant completes the intervention period, their data will be exported from the Fitrockr database and stored securely at the University of Copenhagen server.

During the study, with participants' verbal consent, telephone MI (and control) sessions is audiotaped on a regular basis to ensure fidelity of intervention delivery and to provide counselor feedback.

The participant reported outcomes for the secondary outcomes will be administered using SurveyXact, securing data every time a survey has been completed. Every time a participant completes the intervention period, their data will be exported from the Fitrockr database and stored securely at the University of Copenhagen server.

No personal data will be exported from Fitrockr or SurveyXact without pseudonymization. Complete anonymization of all data will be done after the last follow up period. Data protection agency approval Reference number: 514-0268/18-3000

20. Statistical methods

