The primary outcome will be analyzed as a mixed effects model, where intervention group are analyzed fixed and participants are random effects. The analysis will investigate the group difference in average daily step count, adjusted for baseline step count and gender. Same analysis will be performed on secondary outcomes.

Drop outs with data on the primary outcome for at least one week will have their average daily step count based on the available days. All analysis will be performed following the Intention to Treat (ITT) principle imputing missing data using a multiple imputation based on age, gender, baseline step counts and average daily step count (for missing data on the secondary outcomes). In

calculating the average daily step count, days with less than 100 steps will be handled as “days of non-wear” and excluded assessing the mean step count.

Methods: Monitoring

21. Data monitoring

Not applicable/relevant

22. Harms

In our study an adverse event will be defined as any untoward medical occurrence in a participant without regard to the possibility of a causal relationship with the intervention. Adverse events will be collected after the subject has provided consent and enrolled in the study. If a participant experiences an adverse event after the electronically administered informed consent has been signed (entry) but the subject has not started to receive study intervention, the event will be reported as not related to the intervention. All adverse events occurring after entry into the study will be recorded. The participants will be asked at the end-point questionnaire if they experienced any adverse events in terms of using the PAMs or trying to enhance their daily amount of physical activity.

23. Auditing

No auditing has been protocolled.

Ethics and dissemination

24. Research ethics approval

According to a written correspondence with the Danish Ethics Committee in the Capital Region of Denmark, this trial was not subject to the current laws on research ethics in Denmark due to the non-invasive behavioral change intervention. The study can be conducted without further approval from the Danish Ethics Committee in the Capital Region of Denmark (Journal-nr.:18004960).

25. Protocol amendments

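### The questionnaire imputation list leaves out treatment arm and the own baseline score, and the plan does not say whether the analysis adjusts each questionnaire for its own baseline

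*Combined protocol and SAP*

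**What the plan says.** Section 20 (Statistical methods) sets out one mixed model, with intervention group fixed and participant random. It estimates the group difference in average daily steps "adjusted for baseline step count and gender". For the questionnaires it adds one sentence: "Same analysis will be performed on secondary outcomes".

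Missing data are handled by "multiple imputation based on age, gender, baseline step counts and average daily step count", the last variable being marked as for the secondary outcomes. No other section adds treatment arm or a questionnaire's own baseline score to either model.

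Other relevant places:

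- **Section 7, hypothesis 2:** motivational interviewing "will affect self-reported physical activity and quality of life".
- **Section 12:** all seven questionnaires are collected at baseline, 12 weeks, 6 months and 12 months.
- **Section 14:** 128 participants are needed to detect 0.5 SD. "To account for attrition this study will include 20% more participants than the above mentioned", which gives 154.
- **Section 17b:** "neither participants nor staff conducting the motivational interview in the intervention group can be blinded to allocation". For the analyst, "The group names of the intervention and the control group will be anonymized before the data will be analyzed".
- **Section 18a:** "All participants will receive an email with an electronic SurveyXact invitation on the day of randomization".

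**The concern.** There are two separate points.

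**Imputation.** An imputation model should contain the variable whose effect is being estimated. Without arm, the imputed scores in both groups are drawn from one common regression and differ between groups only as far as steps differ. Mixing them with observed scores pulls any true questionnaire difference toward zero. Rubin's standard error does not shrink to match, so power falls as well. Omitting the own baseline score discards what is probably the best predictor of the missing value.

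**Analysis.** Read literally, a quality-of-life or loneliness score is adjusted for baseline steps but not for its own baseline. That does not bias a randomized comparison, but it gives up precision. Because baseline steps are the own baseline of the primary outcome, the sentence may instead mean that each outcome is adjusted for its own baseline. The text does not say which.

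At stake are the contrasts behind hypothesis 2. The covariates of the primary model are not questioned, and nothing is claimed about the mediation in hypothesis 3.

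**Working it through.** **The plan's own figure.** A two-sample t-test for 0.5 SD, two-sided 0.05 and 80% power needs 63.77, so 64 per arm, or 128. Then 128 × 1.2 = 153.6, or 154 (77 per arm). Both stated figures reproduce.

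**Assumptions.** The documents give neither a questionnaire missing rate nor a baseline-to-follow-up correlation r.

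- Missing scores: 154 − 128 = 26 (17%), with 15 and 46 as alternatives, missing completely at random.
- r: the IPAQ-SF reliability range in Section 12, 0.32 to 0.88, is used as a proxy for all seven instruments, with 0.6 as a mid-range value.
- Steps and scores correlate 0.3, the size of the pooled IPAQ-SF correlation with accelerometry in Section 12. In-trial steps correlate 0.8 with baseline steps.
- True questionnaire difference: 0.50 SD at one visit.

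**1. Imputation.** Simulation of 4,000 trials, 20 imputations, Rubin's rules, power by |z| > 1.96, r = 0.6, 26 missing, no step difference between arms:

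| Imputation model | Analysis model | Estimate (SD) | Mean SE | Power |
|---|---|---|---|---|
| as listed | as written | 0.411 | 0.171 | 71% |
| as listed | + own baseline | 0.413 | 0.156 | 81% |
| + own baseline | + own baseline | 0.413 | 0.143 | 87% |
| + arm | as written | 0.497 | 0.171 | 83% |
| + arm | + own baseline | 0.499 | 0.156 | 89% |
| + arm, own baseline | + own baseline | 0.500 | 0.143 | 94% |

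Monte Carlo error of the estimates is about 0.002. As a rough check, if imputed scores carry no difference, the expected estimate is 0.50 × 128/154 = 0.416.

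The table separates two effects. Only arm removes the bias: with own baseline in both models but no arm, the estimate stays at 0.413. Own baseline lowers the standard error.

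Sensitivity of the as-listed plan:

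- 15 missing: 0.452. 46 missing: 0.345.
- r = 0.32 or 0.88 (2,000 trials): 0.417 or 0.410, so the bias hardly depends on r.
- In-trial steps also differing by 0.5 SD between arms: 0.439. With own baseline in both models and still no arm it is 0.432; with arm and own baseline it is 0.500.
- No true difference: estimate 0.002 and rejection rate 1.7%, against 4.5% with arm and own baseline in both models. There is no bias, but the test is conservative.

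A variant simulation (1,500 trials, slightly different step correlations) with 10%, 20% and 30% missing gives 0.447, 0.398 and 0.349 SD as listed, or 0.472, 0.444 and 0.414 SD if steps also differ by 0.5 SD. At 20% missing with no step difference, the estimates have an actual SD of 0.144 but a mean reported SE of 0.179. This shows why the test is conservative.

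**2. Own baseline in the analysis, complete data, 77 per arm.** SE = √(2 × residual variance / 77).

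- Steps only: residual variance 1 − 0.3² = 0.91, SE 0.154.
- Steps and own baseline: residual variance 1 − (r² + 0.09 − 0.18r)/0.91 = 0.852, 0.624 and 0.224 at r = 0.32, 0.6 and 0.88. SE 0.149, 0.127 and 0.076.

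The interval is therefore 3%, 17% or 50% narrower, 50% being the extreme end. At r = 0.6, a steps correlation of 0 or 0.5 changes the gain to 20% or 12%.

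If a change-from-baseline analysis was intended, SE = √(4(1 − r)/77) = 0.188, 0.144 and 0.079, and the gain from own-baseline adjustment is 21%, 12% or 3%.

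**The case against.** **The sentence on secondary outcomes may already mean own-baseline adjustment.** This stands. The analysis half is a request to state the intent, and its gain is zero if that was the intent. Power should then be compared within the own-baseline rows of the table: 87% without arm and 94% with it, when own baseline is in both models.

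**A participant random effect suggests a repeated-measures model with the baseline score among the outcomes.** This is possible, and the text does not settle it. All figures here are for one visit. The reading would not put arm into the imputation list.

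**The list may not be exhaustive.** If arm is used without being listed, or imputation is run separately by arm, the bias is zero. But the list is specific enough to name an extra variable for the secondary outcomes, and an analyst following it would leave arm out.

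**The size is overstated.** In part, yes. The step from 71% to 94% combines changes; arm alone takes it from 71% to 83%. If steps also differ by 0.5 SD, power is about 74% as listed and 80% with arm, roughly six points. The 0.50 SD questionnaire effect and the 26 missing scores are borrowed from the sample-size section. The proxy correlations are unsupported for most of the instruments, and the steps correlation was not varied in the imputation simulation.

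**One continuous score does not represent all seven outcomes.** This stands. Section 12 also categorizes IPAQ-SF into three levels and describes no total score for the social relations questionnaire.

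**The consequences are limited.** Only secondary outcomes are affected, the bias is toward no difference, and no extra false positives arise.

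**Conclusion.** The concern holds. As written, the imputation list omits arm and own baseline score. Following it would shrink a true questionnaire difference by about the share of scores imputed, less where steps also differ between arms. With 26 of 154 missing, 0.50 SD becomes 0.41 SD, or 0.44 SD with a 0.5 SD step difference. The direction is firm whenever a true difference exists that steps do not fully explain. The size rests on assumed missingness, random missingness and assumed correlations.

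The own-baseline covariate in the analysis is a point of clarity. Under the literal reading it costs 3% to 50% in interval width, 17% at r = 0.6.

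This should be corrected before analysis, but it does not touch the primary comparison.

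**What to change.** Add two sentences to Section 20:

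- *Each secondary outcome will be analysed with its own baseline score, baseline step count and sex as covariates.*
- *Missing secondary outcomes will be imputed from treatment group, the outcome's own baseline score, age, sex, baseline step count and average daily step count.*

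The coded group label is sufficient for the imputation, so the analyst stays blinded. The plan should also name the score analysed for each questionnaire and say how a missing baseline questionnaire is handled.

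One safeguard is needed. The baseline survey is sent on the day of randomization to participants who are not blinded. Section 12 places it before the first interview, but no section says when participants learn their allocation. Either have the survey completed before allocation is disclosed, or report a sensitivity analysis in all participants without the own baseline score in either model.

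The cost is a few sentences of SAP text, using data already collected. Completing the survey before disclosure would change a procedure; the sensitivity analysis avoids that and needs no completion times.

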The project telephone counselor has a masters degree in physiotherapy and additional training in the MI approach to telephone health behavior counseling. Training involved a four-day course, reading study materials, discussions with previous study investigators, viewing of MI recording, and roll plays. Prior to this study the counselor has also conducted more than 200 interviews with older adults and staff in the community to familiarize with the community culture and local resources.

During the study, with participants' verbal consent, telephone MI (and control) sessions is audiotaped on a regular basis to ensure fidelity of intervention delivery and to provide counselor feedback. Based on a review of these recordings the fidelity monitoring is conducted by two experienced independent MI coders who are blinded to treatment assignment using the Motivational Interviewing Treatment Integrity (MITI) Scale, a tool developed to measure MI treatment adherence [30].

12. Outcomes

Primary Outcome Measure:

1. Individual intervention period average steps per day, recorded every day by the PAM. The average number of steps per day throughout the 12 weeks will be the primary outcome for the individual participant.

Time frame: A daily average of the 12 weeks of intervention

The Garmin Vivofit 3 will serve as the PAM and thus, measure the primary outcome. Garmin Vivofit 3 has to our knowledge only been validated in older adults by our own research group (manuscript being prepared for submission).

Four physical activity monitors were included in the validation study; Misfit Shine, Nokia GO, Jawbone UP and Garmin Vivofit 3. The aim of the study was to compare different PAMs on different body locations. All hip-worn PAMs fulfilled the a priori hypothesized moderate criterion validity, when evaluating all participants. The hip-worn Garmin Vivofit 3 fulfilled the a priori

hypothesized criterion validity evaluating all participants, participants with rollator and participants without rollators and it was evaluated as the best performing device in older adults in general.

The validation study is currently being finalized for submission.

Secondary Outcome Measures:

1. International Physical Activity Questionnaire [Time Frame: Baseline + end point at 12 weeks + follow up at 6 months and 12 months]
2. Nordic Physical Activity Questionnaire [Time Frame: Baseline + end point at 12 weeks + follow up at 6 months and 12 months]

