3. EQ5D Quality of life questionnaire [Time Frame: Baseline + end point at 12 weeks + follow up at 6 months and 12 months]
4. UCLA Loneliness Scale [Time Frame: Baseline + end point at 12 weeks + follow up at 6 months and 12 months]
5. Self-Efficacy for Exercise [Time Frame: Baseline + end point at 12 weeks + follow up at 6 months and 12 months]
6. Outcome expectancy for Exercise-2 [Time Frame: Baseline + end point at 12 weeks + follow up at 6 months and 12 months]
7. Copenhagen Social Relations Questionnaire [Time Frame: Baseline + end point at 12 weeks + follow up at 6 months and 12 months]

Secondary outcome measures include participant reported outcomes administered by online questionnaires. The baseline measurement will be undertaken before the intervention group receives the first motivational interview and the end point measurement will be undertaken in the days after the last motivational interview.

International Physical Activity Questionnaire short form (IPAQ-SF)

The seven-item IPAQ-SF measure assesses the types of intensity of physical activity and sitting time that people has done the past seven days as part of their daily lives are considered to estimate total physical activity in MET-min/week and time spent sitting [31]. The score is categorized to three levels of (categories) of PA; low, moderate and high [32]. In a review of 16 international studies of

the measurement properties IPAQ-SF showed acceptable reliability (Spearman's rho: 0,32-0,88) [31] and low to moderate concurrent validity against accelerometer had a pooled correlation coefficient of 0.30 (Spearman's rho range: 0,09-0,38) [33]. The Danish version have been used in a Danish population of older adults [34].

Nordic Physical Activity Questionnaire short (NPAQ-short)

The two-item NPAQ-short [35] is a short revised version of the original NPAQ, a survey tool based on telephone interviews designed for assessment of Moderate and Vigorous Physical Activity (MVPA). It is developed to monitor compliance with the WHO recommendations on PA [36] and has showed moderate correlation with objectively measured MVPA (Spearman's rho: 0.33) in a Danish population with an average age of 43 (range: 17-85) [35].

The 5-level EuroQol-5 Domain (EQ-5D-5L) Quality of life questionnaire

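### Section 20 carries the step-count model over to questionnaires measured at several occasions without saying which occasion is tested, whether occasions are fitted jointly, or that the questionnaire's own baseline score is used

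*Combined protocol and SAP*

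**What the plan says.** Section 20 (Statistical methods) describes one model for the primary outcome, a "mixed effects model, where intervention group are analyzed fixed and participants are random effects", "adjusted for baseline step count and gender". For the questionnaires it adds one sentence: "Same analysis will be performed on secondary outcomes".

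The two kinds of outcome have different structures. Under Sections 12 and 18a, the daily step totals are reduced to one average per participant over the 12 weeks. Each of the seven questionnaires in Section 12 has the time frame "Baseline + end point at 12 weeks + follow up at 6 months and 12 months".

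On timing, Section 12 says that "the end point measurement will be undertaken in the days after the last motivational interview" and that "The secondary outcomes will also serve as follow up measurements six and 12 months after ending the intervention". Hypothesis 2 in Section 7 says that the interviews will affect self-reported activity and quality of life, and gives no time point.

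No section writes a time effect, a group-by-time term, a contrast at a given occasion, or an occasion at which the questionnaires are tested. The only baseline adjustment written for them is baseline step count.

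**The concern.** A model written for one value per person is applied, with nothing added, to outcomes with three post-randomisation values and a baseline score. An analyst following Section 20 has to choose between two readings, and neither works as written.

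- **Occasions stacked in one model.** Group is the only effect of interest, so the model returns one difference averaged over the end of the intervention and two later follow-ups. An effect present at 12 weeks that fades is diluted. The model also has no term that could show whether the effect lasts, which is the natural use of the 6- and 12-month data.
- **Each occasion fitted alone.** The 12-week difference can be obtained, but the participant random effect has no repeated values to be estimated from. The plan also does not say which occasion decides hypothesis 2.

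Under both readings the written covariate is baseline steps. The questionnaire's own baseline score, which is already collected and is the natural covariate, is left out.

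**Working it through.** **1. The plan's own figure.** Section 14 gives 128 participants for a 0.5 SD difference, 80% power and significance level 0.05. A two-sided two-sample t-test needs 63.77 per arm, so 64 per arm and 128 in total, with power 80.1%. The figure reproduces. It is used here only to set 64 per arm; Section 14 does not link the 0.5 SD to any questionnaire.

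**2. Inputs not in the documents.** The effects at follow-up and the within-person correlation (rho) are not given. Both are assumptions, shown over a range.

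**3. Stacked reading, three post-baseline occasions.** With complete, balanced data and a random intercept, the group coefficient is the simple mean of the occasion-specific differences. In SD units, for m occasions and 64 per arm:

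SE = sqrt( [(1 + (m − 1) × rho) / m] × 2/64 )

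Take differences of 0.5 (12 weeks), 0.25 (6 months) and 0 (12 months), with rho = 0.6:

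- Estimate: (0.5 + 0.25 + 0)/3 = 0.25 SD
- SE: sqrt( (2.2/3) × 0.03125 ) = 0.151
- Power: Φ(0.25/0.151 − 1.96) = Φ(−0.31) ≈ 38%

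**4. The 12-week contrast in the same scenario.** SE = sqrt(2/64) = 0.177, and power = Φ(0.5/0.177 − 1.96) = Φ(0.87) ≈ 81% by the normal approximation (80.1% by the t-test). The estimate is 0.5 SD.

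**5. Range.** The 12-week difference is 0.5 SD throughout, and power for the 12-week contrast is about 80% in every row.

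| Assumed differences at 12 weeks / 6 months / 12 months | Stacked estimate (SD) | Power, rho 0.3 | rho 0.5 | rho 0.7 |
|---|---|---|---|---|
| 0.5 / 0.5 / 0.5 | 0.50 | 97% | 93% | 89% |
| 0.5 / 0.25 / 0.25 | 0.33 | 73% | 64% | 56% |
| 0.5 / 0.25 / 0 | 0.25 | 49% | 41% | 35% |
| 0.5 / 0 / 0 | 0.17 | 25% | 21% | 18% |

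The stacked coefficient equals the 12-week difference only in the first row.

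**6. Separate reading.** With one row per participant, the random-intercept variance and the residual variance enter only as their sum, so they cannot be told apart. The group coefficient can still be estimated and is that of an ordinary regression, so this is a fault of specification and not a bias. What stays open is the choice of result: three post-baseline occasions for seven questionnaires is 3 × 7 = 21 group differences, with none named as the main one.

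**7. Baseline adjustment.** Adjusting for a covariate that has correlation r with the outcome multiplies the residual variance by 1 − r². If a questionnaire's baseline score has r = 0.6 with its 12-week score, the factor is 1 − 0.36 = 0.64. The SE of the 12-week contrast is then sqrt(0.64 × 2/64) = 0.141, and power for 0.5 SD is Φ(0.5/0.141 − 1.96) ≈ 94%. For r of 0.3, 0.5 and 0.7 the same formula gives 84%, 90% and 98%.

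**The case against.** The strongest objection is that stacking is nowhere written. A reader might infer that the plan pools the occasions, because a participant random effect has a purpose only with repeated values. The documents do not support that as a statement of fact. Section 20 writes the same random effect for step count, which has one value per person, so its presence says little about how the questionnaires will be handled. Section 12 labels the 12-week and later measurements separately, which fits one model per occasion equally well. On that reading there is no dilution. This stands, and the dilution figures are therefore conditional on stacking.

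Other stronger readings also fail:

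- **Baseline scores entered as outcome rows.** A reader might fear this would dilute the estimate further. Nothing in the plan suggests it; the written analysis treats a baseline value as a covariate.
- **A difference seen only at follow-up is not an intervention effect.** In a randomised comparison it is an effect of assignment. Averaging would misdescribe only its timing.
- **A time trend shared by both arms harms the group estimate.** With balanced data, which the planned imputation would supply, this is of almost no consequence for the group coefficient.
- **The plan already designates the 12-week contrast as the secondary estimand.** Section 12 uses the term end point for the end-of-intervention questionnaire, but lists all occasions in every time frame, and hypothesis 2 names no time.

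It is also fair to say that the fading pattern and the correlation are assumed, and that with a constant effect the stacked estimate is unbiased and more powerful than the 12-week contrast (89% to 97% in the table). The plan does not state such an assumption, and its background section treats lasting change in activity as something still to be secured.

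**Conclusion.** The point holds as a gap in specification with consequences for method. Section 20 does not determine how the questionnaires are analysed. Followed literally, it gives either a time-averaged difference or a model whose random effect cannot be identified, and in both cases it omits the questionnaire's own baseline score.

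The size depends on the reading. If the post-baseline occasions are stacked and the effect fades from 0.5 to 0.25 to 0 SD (64 per arm, correlation 0.6), the reported difference is half the 12-week difference and power is about 38% against about 80%. Over the assumed patterns and correlations of 0.3 to 0.7, the stacked estimate runs from 0.17 to 0.50 SD. If occasions are fitted separately, nothing is diluted, and the cost is an undeclared choice among occasions.

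The point concerns the secondary outcomes on which hypothesis 2 rests. It does not touch the primary step-count comparison or the sample size. It should be corrected before the analysis.

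**What to change.** In Section 20, replace the sentence on secondary outcomes with a statement along these lines:

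- For each questionnaire, the 12-week, 6-month and 12-month values are analysed in a mixed model with group, categorical time and group-by-time as fixed effects and participant as a random effect, adjusted for that questionnaire's baseline score, baseline step count and gender.
- The 12-week group contrast is the main secondary result. The 6- and 12-month contrasts are reported as maintenance results.

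Separate regressions per occasion, each adjusted for the questionnaire's baseline score and without a participant random effect, would also serve if the 12-week occasion is named first.

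The cost is about two sentences. All the data, including the baseline scores, are already scheduled for collection.
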